2.5.3 Handling of missing values/censoring/discontinuations

For the primary analysis, missing data will not be imputed, but various sensitivity analyses (see below) under missing at random and missing not at random assumptions will be performed.

2.5.4 Sensitivity analyses

Analysis of the primary efficacy variable at week 12 will be repeated using an analysis of covariance (ANCOVA) model including treatment group and stratification factor as fixed effects in the model with baseline value as covariate.

Missing data at Week 12 will be imputed using its baseline value (baseline observations carried forward BOCF). In addition, multiple imputation (MI) techniques applying missing at random (MAR) and missing not at random (MNAR) approaches will be used to assess the impact of

| | Page 34 |
|-----------------|--------------|
| SAP Amendment 1 | CAMG334A2302 |

missing values on the interpretation of the results during the DBTP (the imputation methods are described in Section 5.1.5.3).

2.5.5 Supplementary analyses

See Section 2.6.5 for subgroup analysis.

Blinded review of the data identified a number of cases of long lasting headache/ migraine event in multiple patients across different time points during the study. Some subjects reported headaches lasting more than 10 days.

According to the ICHD-3, migraine events are typically of duration 4-72 hours. At time of the assessment of the impact, a significant proportion of events greater than 96 hours were confirmed as due to data entry error or device problems. After further discussion with the Clinical Trial Team (CTT), it was decided to perform supplementary analyses to assess the impact of long lasting headaches (greater than 96 hours) on primary endpoint following adjustment of the duration of these events.

Definition of the modified Monthly migraine days (mMMD):

A modified migraine day is defined as any calendar day in which the patient experiences a qualified migraine headache (onset, continuation, or recurrence of the migraine headache). Please see exceptions in Appendix 5.11. In case the event is lasting more than 96h, days of that event beyond 96h after the start date of the headache event will not be counted as migraine day, eDiary day or information day except if on the end date another headache started (in that case that day only is still counted).

The modified Monthly migraine days is the number of modified migraine days between each monthly IP dose that are normalized in a 28-day interval using the modified number of information days (if the number of modified eDiary days>=14).

For example if a subject had a long-lasting headache starting on 1st June2019 at 11:45pm (Day 1) and ending on 9th June 2019 at 10:30am (Day 9). Projecting forward 96 hours would give the end of the episode as 05June2018 11:45pm (Day 5). Suppose the subject took migraine-specific medications only on Day 6 and no pain/symptoms were associated with the event. Then the event is still classified as a migraine event. Suppose another migraine event started on 9th June 2019 at 5:35pm (Day 9). Only days 2,3,4,5 and day 9 (due to the other event) will contribute to mMMD and to the number of modified information days. If any eDiary reported on those days (day 1, 2, 3, 4, 5, 9) then they will contribute to the number of modified eDiary days.

The change from baseline in mMMD at each month of the DBTP will be analysed in the same way as the primary endpoint (summary statistics, linear mixed effects repeated measures model).

If the supplementary analysis leads to a different conclusion than the primary analysis, further analysis might be considered.

Blinded review of the data identified that due to an issue in the vendor derivation a few cases of patients who were randomized althought the baseline MMD was higher than 14 days. Supplementary analysis will be performed on the subgroup of patients with baseline MMD<15

to assess the impact of those deviations on the primary analysis results for primary endpoints. If the supplementary analysis leads to a different conclusion than the primary analysis, further analysis might be considered.

2.6 Analysis of secondary efficacy objective(s)

2.6.1 Secondary endpoints

The secondary efficacy variables (all during the DBTP) are:

- Proportion of patients who achieve at least a 50% reduction from baseline in monthly migraine days in the last month of DBTP (Month 3).
- Change from baseline in monthly acute migraine-specific treatment days in Month 3 of the DBTP (in the group of patients with at least one acute migraine-specific medication use during baseline)
- Change from baseline in headache impact scores as measured by the HIT-6 in Month 3 of the DBTP

2.6.2 Statistical hypothesis, model, and method of analysis

Analysis of secondary efficacy endpoints will utilize the FAS except for the analysis of change from baseline in monthly acute migraine-specific treatment days in Month 3 of the DBTP, which will be conducted based on the subgroup of patients who used acute migraine-specific medication during baseline. Subjects will be analyzed according to their randomized treatment group regardless of the actual treatment received during the study.

The above continuous change from baseline efficacy endpoints will be analyzed using a linear mixed effects repeated measures model with treatment group, baseline value, stratification factor, scheduled visit, and the interaction of treatment group with scheduled visit, without any imputation for missing data. If applicable, in the repeated statement, an unstructured covariance matrix will be used.

The dichotomous endpoint (Proportion of patients who achieve at least a 50% reduction from baseline in monthly migraine days in the last month of DBTP) will be analyzed based on Cochran-Mantel-Haenszel (CMH) test after patients who have missing monthly migraine day data at Month 3 of the DBTP imputed as non-responders.

The description of the models can be found in Section 5.4.

In all cases, estimates (difference or odds ratio) of treatment group compared to placebo group with associated nominal 95% confidence intervals and nominal two-sided p-values will be provided.

A hierarchical gate-keeping procedure and the Hochberg method will be used to maintain the overall 2-sided study-wise type I error rate at 0.05 for the primary endpoint and secondary efficacy endpoints. The primary endpoint, the change from baseline in monthly migraine days

to the last 4 weeks of the 12-week double-blind treatment period, will be initially tested at a 2sided significance level of 0.025 for each of the AMG 334 treatment group (140 mg and 70 mg) compared to the placebo group, respectively. If the primary endpoint and all secondary endpoints are statistically significant for an AMG 334 treatment group, the corresponding significance level will be carried over to the primary endpoint for the other AMG 334 treatment group, and the primary endpoint will be re-compared to the placebo group at a 2-sided significance level of 0.05 (full alpha). If the primary endpoint of one dose group is statistically significant but not all the secondary endpoints, only half of the initial alpha of the dose (0.0125) can be transferred to the primary endpoint of the other dose.

Figure 2-1a describes the originally planned testing sequence. But based on the observed data, the testing strategy as per figure 2-1b is thought be more appropriate and will be used for analysis.

$\alpha/2$ $\alpha/2$ Primary endpoint 70mg 1/2 Primary endpoint 140mg Change from baseline of MMD at Change from baseline of MMD at month 3 month 3 1 1/21/2Secondary endpoint 70mg Secondary endpoint 140mg 1 50% MMD responder at month 3 50% MMD responder at month 3 Change from baseline of acute Change from baseline of acute migraine-specific treatment days at migraine-specific treatment days at month 3 month 3 Change from baseline of HIT-6 at Change from baseline of HIT-6 at • month 3 month 3 Use Hochberg method Use Hochberg method

Figure 2-1a Hierarchical Testing Procedure

Figure 2-2b Hierarchical Testing Procedure - Updated

2.6.3 Handling of missing values/censoring/discontinuations

For the proportion of patients who achieve at least a 50% reduction from baseline in monthly migraine days in the last month of DBTP (Month 3), the missing data will be imputed as non-responder (NRI).

2.6.4 Sensitivity analyses

In order to assess the robustness of the analysis for the secondary endpoint "Proportion of patients who achieve at least a 50% reduction from baseline in monthly migraine days in the last month of DBTP (Month 3)", next analysis will be done:

• Logistic regression analysis will be used to get odds ratio of each AMG 334 group vs placebo in the 50% response rate after the missing data are imputed as non-response.

In all cases, the odds ratio of each treatment group compared to placebo group with associated 95% confidence intervals and p-values will be provided.

Detailed secondary efficacy analysis methods, sensitivity analyses, and covariates included in the models are summarized in the table below.

Table 2-4 Summary of secondary efficacy Endpoints and Analysis Methods during DBTP

| Endpoint | Primary Summary and Analysis Method | Sensitivity Analysis |
|----------|--|----------------------|
|----------|--|----------------------|

| The achievement of at least a 50% reduction from baseline in monthly migraine days in the last month of the double-blind period | Analysis Method I: 1. Summary statistics by visit using observed data 2. A stratified Cochran- Mantel-Haenszel (CMH) test will be used after the missing data are imputed as non-response | Analysis method III , NRI: analyze using a logistic regression model that includes treatment and stratification factor as fixed effects and baseline monthly migraine days as covariate |
|--|---|--|
| Change from baseline in monthly acute migraine- specific medication treatment days in the last month of the double-blind period | Analysis method II: 1. Summary statistics by visit using observed data 2. Least squares mean at each time point calculated based on a linear mixed effects repeated measures model including treatment group, baseline value, stratification factor, scheduled visit, and the interaction of treatment group with scheduled visit using observed data. In repeated statement, an unstructured covariance matrix structure will be used. 3. Test pairwise treatment difference (each AMG 334 dose group vs placebo), using a contrast from the model above. | N.A. |
| Change from baseline in headache impact scores as measured by the HIT-6 in the last month of the double- blind period | Analysis method II. | N.A. |

2.6.5 Supplementary analyses

2.6.5.1 Subgroup analyses

The primary and secondary efficacy endpoints will be analyzed at week 12 for the following subgroups that are defined by categorical variables at baseline:

- Prior prophylactic migraine medication treatment failure (prior prophylactic migraine treatment failure, due to efficacy or tolerability, vs no prior prophylactic migraine treatment failure)
- Number of prior prophylactic migraine treatment failure medications: >=2,<2
- Age (< median vs \geq median)
- BMI (< median vs \geq median)
- Sex (Male vs Female)
- Region:
 - Asia (excluding India, Taiwan, Korea)
 - o India
 - o Taiwan
 - o Korea
 - o Others

The effect of other baseline variables, maybe investigated with respect to the primary and secondary efficacy analyses if, upon clinical review, differences between treatment groups are deemed clinically meaningful.

The purpose of the subgroup analyses is to explore if the treatment effect varies across subgroups of interest. Subgroup analyses are performed for primary and secondary efficacy endpoints using the same method as primary analysis method but performed within each subgroup of interest. The treatment difference (or odds ratio) with associated 95% confidence intervals and p-values will be reported within each subgroup.

Note: if the subgroup is the stratification factor (Prior prophylactic migraine medication treatment failure) then the stratification factor will not be included in the model.

The heterogeneity of the treatment effect across the subgroups will be evaluated for the primary and secondary endpoints by examining the treatment by subgroup interaction at primary time point (Week 12) and a p-value will be presented. For continuous endpoints, the primary analysis model with the addition of subgroup and treatment group by subgroup interaction as two additional effects will be used. For endpoint based on proportions, a logistic regression model that includes treatment group, stratification factor, baseline value, subgroup and treatment group by subgroup interaction will be used.

If the value of the group variable cannot be determined, the subject will be excluded from the corresponding subgroup analysis. For each subgroup analysis, if, in any treatment group, the number of subjects is less than 10 for a subgroup, then only summary statistics will be performed.

The least square means for each treatment group, SE's, difference of LSMs compared to placebo group, and associated 95% CIs for each subgroup and the nominal p-value for subgroup by treatment interaction will be calculated.

The outcome will be displayed in separate forest plot for each endpoint (one symbol for placebo vs AMG334 70mg, one symbol for placebo vs AMG334 140mg, in a combined plot), presenting the following information:

- The number of patients within each subgroup level / treatment arm
- Supporting information such as least squares mean by treatment and subgroup level
- The treatment effect estimate and two-sided 95% confidence interval within each subgroup level (using the BY statement for the primary analysis model).
- The directions which favor placebo or AMG 334 will be indicated.
- For pre-specified subgroup analyses, the p-value for the treatment*subgroup term.

2.7 Safety analyses

For safety endpoints, all randomized subjects who received at least one dose of investigational product (i.e., utilizing the SAF) will be analyzed based on the actual treatment received (defined as the randomized treatment unless a subject has received the incorrect dose the entire DBTP).

All safety analyses will be performed for the Double-Blind Treatment Period and Safety Follow-up Period separately.

No statistical testing comparing treatment groups will be performed in the safety analyses.

Missing data will not be imputed for safety endpoints.

2.7.1 Adverse events (AEs)

The Medical Dictionary for Regulatory Activities (MedDRA) version 20.0 or later will be used to code all adverse events (AE) to a system organ class (SOC) and a preferred term (PT). All adverse events will be graded using the Common Terminology Criteria for Adverse Events (CTCAE) Version 4 or higher. All adverse event tables will be summarized by treatment group.

For all AEs tables presented by SOC and PT (and grade), the SOCs will be presented in alphabetical order and PTs will be ordered within the SOC by decreasing order of frequency in the AMG 334 140 mg treatment group.

AE tables by preferred term only will be sorted in descending order of frequency in the AMG 334 140 mg treatment group.

Note, for exposure-adjusted AEs the sorting will be based on the exposure-adjusted subject incidence rate.

Overall subject incidence of AEs and exposure-adjusted subject incidence will be summarized for all treatment-emergent AEs (TEAEs), serious AEs, AEs leading to discontinuation of study treatment and deaths for the DBTP. Summary will be repeated for the safety follow-up period and for the entire study period using subject incidence.

Subject incidence and exposure-adjusted subject incidence of all treatment-emergent AEs, serious AEs, AEs leading to discontinuation of study treatment, serious AEs leading to discontinuation of study treatment and deaths will be tabulated by system organ class and preferred term for DBTP. Summaries will be repeated for the safety follow-up period using subject incidence.

In addition, subject incidence and exposure-adjusted subject incidence of all treatmentemergent AEs will be tabulated by SOC, PT and CTCAE grade for the DBTP. Summaries will be repeated for the safety follow-up period using subject incidence.

Subject incidence and exposure-adjusted subject incidence of all TEAEs and serious AEs will be tabulated by PT for the DBTP. Summaries will be repeated for the safety follow-up period using subject incidence.

Subject incidence all treatment-related AEs and serious treatment-related AEs will be tabulated by SOC and PT for the DBTP.

All AEs, deaths (see Section 2.7.2 for details), SAEs and AEs leading to permanent study drug discontinuation will be listed separately.

2.7.1.1 Adverse events of special interest / grouping of AEs

Not applicable.

2.7.2 Deaths

Deaths will be listed by treatment including the start date of the study treatment, the last date on study treatment, the death date and the primary cause (and contributing cause if any) for death.

2.7.3 Laboratory data

Summary statistics will be presented for absolute as well as change from baseline of laboratory hematology, blood chemistry results by visit, treatment and laboratory test category.

Subject incidence of newly occurring liver enzyme abnormalities (including AST, ALT, Total Bilirubin (TBL) and Alkaline Phosphatase (ALP)) will also be summarized by treatment group and study phase (separately for the DBTP and follow-up period.).

Shift from baseline for some liver enzyme level categories (specified in the TFL shells; for e.g. ALP<=1 x ULN) will also be provided by treatment group and study phase (separately for the DBTP and follow-up period).

Clinically notable laboratory values will be flagged and listed by treatment.

Parameters measured in the urine at screening including urine drug tests (if applicable) will be listed.

2.7.4 Other safety data

Serum pregnancy test results (if applicable) will be listed for female patients.

2.7.4.1 ECG data

The ECG measurements from this clinical study will be performed as per standard of care for routine safety monitoring, rather than for purposes of assessment of potential QTc effect.

Subject incidence of abnormal ECG diagnosis (see Table 5-5) will be summarized by treatment group and by visit, for the DBTP.

ECG measurements will be listed by treatment.

However, since these evaluations may not necessarily be performed under the rigorous conditions expected to lead to meaningful evaluation of QTc data, these data are not expected to be useful for meta-analysis with data from other trials.

2.7.4.2 Vital signs and weight

The analyses of vital signs (systolic/diastolic blood pressure, pulse rate) and weight will include summary statistics of change from baseline by treatment group and by visit, for DBTP and for safety follow-up period.

The number and percentage of patients with clinically relevant abnormality (see Table 5-3) at any post-baseline visit will be presented, separately for DBTP and for safety follow-up period.

Patient listings (including systolic/diastolic blood pressure, pulse rate and temperature measurements) will be provided and values outside these critical value ranges will be flagged.

2.7.4.3 Columbia-Suicide Severity Rating Scale (C-SSRS)

The number and percentage of subjects reporting any suicidal ideation or any suicidal behavior will be summarized descriptively by treatment group and by visit, for DBTP and for safety follow-up period, respectively.

Shift table of C-SSRS maximum severity of suicidal ideation/behavior compared to baseline will be provided by treatment group for DBTP and for safety follow-up period, respectively.

No statistical testing will be performed on C-SSRS.

2.7.4.4 Anti – AMG 334 Antibody Formation - Immunogenicity (IG) analysis set

The number and percentage of subjects who are positive for anti-AMG 334 antibodies at baseline (Day 1, pre-dose) and who develop anti-AMG 334 antibodies (binding and, if positive, neutralizing) at any time during the study (after signing informed consent and up to the end of the DBTP) will be tabulated by treatment group.

In addition, the number and percentage of patients who develop anti-AMG 334 antibodies at any time post-dose during the DBTP (Visit 130, 150 and 1999) will be tabulated by treatment group.

The list of subjects with positive at any time will be provided.

The Immunogenicity prevalence set includes all patients in the Full analysis set with a determinant baseline IG sample or at least one determinant post-baseline IG sample.

The Immunogenicity incidence set includes all subjects in the Immunogenicity prevalence set with a determinant baseline IG sample and at least one determinant post-baseline IG sample.

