#### Table 6-1Assessment Schedule

Period	Scree	ning	Treatment			Follow-Up		
Visit Name	Screening	Baseline	Treatment	Week 2 	Week 4	Week 8	End of Treatment	Follow-Up
Visit Numbers 	1	20	110	120	130	140	150 and TD/PSD	1999
Days	-42 to -28	-28 to -1	Day 1	14	28	56	84	168
Weeks	-6 to -4	-4 to -1	1	2	4	8	12	24
Informed consent	Х							
Medical history/current medical conditions	Х	Х						
Demography	Х	Х						
Safety Follow up Call				Х				
Physical Examination	Х	Х	Х		Х			Х
Vital signs and body measurements 	Х	Х	Х		Х	Х	Х	Х
Electrocardiogram (ECG)	Х		Х		Х		Х	
Hematology	Х		Х		Х		Х	Х
Clinical Chemistry	Х		Х		Х		Х	Х
Pregnancy Test (serum)	Х						Х	
Pregnancy test (urine)		Х	Х		Х	Х		Х
Urinalysis	Х							
Urine Drug Screen	Х							
Hepatitis screen ₄	Х							
Anti-AMG 334 antibodies			Х		Х		Х	Х
Columbia-Suicide Severity Rating Scale (C-SSRS)	Х	Х	Х		Х	Х	Х	Х
Beck Depression Inventory-II (BDI-II)	Х							
Randomization			Х					
Study drug administration			Х		Х	Х		
Clinical Outcome Assessment(s)					X 			

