1.1 Study design

This study uses a single-cohort, 3-treatment arm, randomized (2:3:3 [140 mg: 70 mg: placebo]), double-blind study design in adult patients with episodic migraine.

The following periods are included in the study design:

- Screening period of 2 weeks: to assess initial eligibility,
- Baseline period of 4 weeks: All patients successfully completing the Screening period are invited to participate. Final eligibility prior to randomization and dosing will be assessed based on headache frequency and diary compliance during this period,
- Double-blind treatment period (12 weeks): All patients successfully completing the Baseline period are invited to participate. Eligible patients will be randomized to one of three treatment arms. After randomization/Day 1, visits will occur at four week intervals until Week 12, which is the End of Treatment visit.
- Safety follow-up period: the final visit, a Safety Follow-Up visit, will occur 12 weeks later, at Week 24.

A blinded interim analysis after approximately 50% patients have completed the DBTP (including early withdrawals) will be conducted to re-estimate the sample size by providing information on the variance for this trial relative to the planning assumptions to account for potential higher variability in Asian countries/new sites.

End of Trial (Last Patient Last Visit, LPLV) will occur when all patients have completed their last visit.

Approximatively 880 patients will be randomized (330 in placebo, 330 in AMG334 70mg and 220 in AMG334 140mg), stratified by prior prophylactic migraine medication treatment failure (prior prophylactic migraine treatment failure, due to efficacy or tolerability, vs no prior prophylactic migraine treatment failure).

The primary analysis and all other efficacy and safety analyses will be conducted at the end of study after the database lock; i.e., at the time point when all patients have completed their last visit.

Figure 1-1 Study Design Schematic

| Screen | Baseline | Double-Blind Treatment | Follow-Up |
|---------|----------|------------------------|-----------|
| 2 weeks | 4 weeks | 12 weeks | 12 weeks |

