For safety analyses which are summarized by study phase (AE, antibody, laboratory, vital signs, ECG and C-SSRS), or during the entire study (anti-AMG334 antibody), analysis windows will be set up based on study phase:

Table 2-2Study Phases for Safety analysis

| | • | • • | | |
|-------------|---|-----------------|-----------------------|--|
| Study Phase | S | tart Time Point | End Time Point | |
| | | | | |

| Double-blind Treatment Period | For AE, concomitant medications: Study Day 1 Otherwise: Study Day 2 | For AE, concomitant medications: MIN (EoS date, last IP dose date + 27 days) Otherwise: MIN(EoS Date, MAX(last IP dose date + 27 days, EoT date+14 days)) |
|----------------------------------|---|--|
| Safety follow-up | For AE, concomitant medications: last IP dose date + 28 days Otherwise: MAX(last IP dose date + 28 days, EoT date+15 days) | For AE, concomitant medications: MIN(EoS Date, last IP dose date + 16 weeks) Otherwise: MIN(EoS Date, last IP dose date + 16 weeks +14 days) |
| Entire Study | For AE, concomitant medications: Study Day 1 Otherwise: Study Day 2 | For AE, concomitant medications: MIN(EoS Date, last IP dose date + 16 weeks) Otherwise: MIN(EoS Date, last IP dose date + 16 weeks +14 days) |

Note: all anti-AMG 334 antibody data during all periods will be included in immunogenicity analysis.

Monthly Interval for Efficacy Endpoints (from eDiary)

Monthly efficacy measurements will be calculated based on the subject's monthly investigational product (IP) dosing schedule defined below using eDiary data collected from beginning of the baseline phase (week -4 visit) up to EOT visit (week 12 visit).

| Study Phase | Assessment Time point | Interval Based on Dose | Dates |
|-------------------------------------|--------------------------|---|--|
| | | Start date | End date |
| Baseline Period | Baseline | From eDiary device assignment date (or Week -4 visit) | Day prior to study day 1 |
| Double-Blind Treatment Period | Week 4 | Study Day 1 | Week 4 dose date-1 Study day 28 if Week 4 dose is not received (either missed or IP discontinued prior to Week 4) |

Table 2-3Study Intervals for Efficacy Endpoints

| | | Note: if day 1 dose is the last IP dose subject received, the rest of monthly rates during DBTP will be calculated based on consecutive 28-day interval beginning on study day 29 (ie, 29-56 for week 8, 57- 84 for week 12) |
|---------|--|--|

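### SAP 2.7.4.4: the antibody table for the whole study stops at the end of the double-blind period, while the double-blind-period table includes the Week 24 follow-up visit

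*SAP*

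**What the plan says.** SAP 2.7.4.4 describes two tabulations by treatment group. The first reports patients positive at baseline and patients who develop antibodies at "any time during the study (after signing informed consent and up to the end of the DBTP"). The second reports patients who develop antibodies "at any time post-dose during the DBTP (Visit 130, 150 and 1999").

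The schedule is clear about Visit 1999. In Protocol Table 6-1, the row "Anti-AMG 334 antibodies" is marked at Visits 110 (Day 1), 130 (Week 4), 150 (Week 12) and 1999 (Week 24), the last of these in the Follow-Up column. SAP 1.1 agrees: "the final visit, a Safety Follow-Up visit, will occur 12 weeks later, at Week 24".

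SAP 2.1.2 already has a framework for antibody data. The lead-in to Table 2-2 reads "For safety analyses which are summarized by study phase (AE, antibody, laboratory, vital signs, ECG and C-SSRS), or during the entire study (anti-AMG334 antibody"), and the table defines double-blind (DBTP), safety follow-up and Entire Study windows. A note below it states that "all anti-AMG 334 antibody data during all periods will be included in immunogenicity analysis". Protocol 9.5.2 asks for antibodies developing at any time, with no cut-off at the end of the DBTP. Protocol 9.5.2 and SAP 2.7 both require safety analyses to be done separately for the two periods.

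On population, SAP 2.7.4.4 draws the prevalence set from the FAS and the incidence set from the prevalence set. SAP 2.7 puts safety endpoints on the SAF, by actual treatment.

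**The concern.** In each table the label and the definition contradict each other, so a programmer must choose which to follow. If the definitions are followed, a baseline-negative patient who first turns positive at Week 24 is counted in the double-blind table and in the overall incidence of SAP 2.7.4.4.2, but not in the whole-study table. Among scheduled post-dose samples, the double-blind count could then exceed the whole-study count, which is impossible if the labels are true. The neighbouring sections on vital signs and C-SSRS split the two periods correctly; this section does not.

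Antibodies are named among the secondary safety endpoints, and a reader of the study report would take the table labels at face value. Drawing the denominators from the FAS also makes a safety summary depend on diary completion.

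**Working it through.** The plan states no figure to reproduce. The check applies the SAP's windows to the sampling schedule.

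**Inputs**
- Sampling days (Protocol Table 6-1): Visit 110 = Day 1, Visit 130 = Day 28, Visit 150 = Day 84, Visit 1999 = Day 168.
- Last dose L: nominally Day 56. With the 5-day tolerance in Protocol 5.5.4, L is Day 51 to 61.
- End of treatment E: nominally Day 84. The range Day 79 to 89 is an assumption.
- Follow-up target (SAP Table 2-1): L + 112 days.
- Table 2-2 rows for data other than adverse events and concomitant medications. DBTP end: "MIN(EoS Date, MAX(last IP dose date + 27 days, EoT date+14 days")). Follow-up start: "MAX(last IP dose date + 28 days, EoT date+15 days"). Follow-up and Entire Study end: L + 112 + 14, or end of study if earlier. End of study is assumed not to come earlier.

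**On-schedule patient (L = 56, E = 84)**
- DBTP end = MAX(56 + 27, 84 + 14) = MAX(83, 98) = Day 98
- Follow-up start = MAX(56 + 28, 84 + 15) = MAX(84, 99) = Day 99
- Follow-up end = 56 + 112 + 14 = Day 182
- Visit 1999 = Day 168, which is 168 − 98 = 70 days after the DBTP ends and inside Days 99 to 182

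**Range for a patient who receives all three doses**
- Smallest gap (L = 51, E = 89): 163 − MAX(78, 103) = 60 days
- Largest gap (L = 61, E = 79): 173 − MAX(88, 93) = 80 days

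**Early stoppers (illustrative cases)**
- One dose on Day 1, E = 28: 113 − MAX(28, 42) = 71 days
- One dose on Day 1, E = 84: 113 − MAX(28, 98) = 15 days
- Last dose on Day 28, E = 84: 140 − MAX(55, 98) = 42 days

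In none of these cases does an on-target Visit 1999 fall in the DBTP.

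**Scheduled post-baseline samples in each table**

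| Table, by its label | As written | Under Table 2-2 |
|---|---|---|
| Whole study | 130, 150 (2 of 3) | 130, 150, 1999 (3 of 3) |
| DBTP | 130, 150, 1999 (3 of 3) | 130, 150 (2 of 3) |
| Follow-up | no such table | 1999 |

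**Population.** SAP Table 5-2 removes from the FAS any dosed patient with no change from baseline in monthly migraine days during the DBTP. SAP 5.1.5.1 sets a month to missing when it has fewer than 14 eDiary days. Eligibility required at least 80% baseline diary compliance, so in practice a dosed patient leaves the FAS only if all three post-baseline months have fewer than 14 eDiary days. A patient who leaves within two weeks of the first dose could still give an antibody sample at the discontinuation visit, which shares the Visit 150 column of Table 6-1, yet would be in neither immunogenicity set.

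**The case against.** The best counter-argument is that nothing is lost. The second table already holds every scheduled post-dose sample, so under another label it would deliver the Protocol 9.5.2 tabulation. The Table 2-2 note brings in data from all periods. SAP 2.7.4.4.2 gives overall incidence with no cut-off and prevalence by time point, so Week 24 appears separately, and there are listings. The analysis is descriptive. The documents do not say which period was intended, and exchanging the two end points would remove both label conflicts without a new table. On population, a set defined for one endpoint can override a general rule. Actual treatment differs from randomized treatment only if the dose was wrong at every visit (SAP 2.2).

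Much of this stands: Week 24 data survive, the second table omits no scheduled sample, and the population effect is probably small. It does not remove the error. The first table still has the wrong content for its label, and the second still mixes periods that the protocol and SAP say to analyse separately. Exchanging the end points would leave follow-up without its own tabulation of newly developed antibodies. Prevalence by time point does not fill that gap, because it also counts patients already positive at baseline. The SAP gives no reason for departing from the SAF.

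**Conclusion.** The concern holds, as a minor error. Followed as written, the whole-study table omits 1 of 3 scheduled post-baseline samples, and the double-blind table includes a visit that falls 70 days after that period ends on schedule. For a fully dosed patient the gap is 60 to 80 days, given the assumed end-of-treatment range. The harm is confined to the content of the first table and to the label and missing period split of the second.

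The number of patients first positive at Week 24 cannot be computed from the documents. Nor can the number in the SAF but outside the FAS. The population point is a real conflict with SAP 2.7, but it is secondary.

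**What to change.** In SAP 2.7.4.4 and the table shells:

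1. End the whole-study tabulation at the Table 2-2 Entire Study end point instead of the end of the DBTP.
2. Remove Visit 1999 from the DBTP tabulation, leaving Visits 130 and 150.
3. Add a separate follow-up tabulation for Visit 1999.
4. Secondary: base the prevalence set on the SAF by actual treatment instead of the FAS. Keep the determinant-sample rules for both immunogenicity sets.

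The cost is two phrase corrections, one small added table and one population flag. No new data are needed, and efficacy testing is unaffected.
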